5. BACKGROUND AND SIGNIFICANCE

Ureteroscopic stone treatment is a minimally invasive procedure commonly performed for kidney stones. Recently, the thulium fiber laser (TFL) has demonstrated effectiveness in this procedure. A new laser system developed by Dornier, the Thulio pulsed Thulium:YAG (p-Tm:YAG) is beginning to be studied *in vitro* (Huusmann et al., 2021; Petzold et al., 2021a, 2021b, 2021c, 2021d; Kraft et al., 2022a, 2022c; Kwok et al., 2023) and *in vivo* (Panthier et al., 2023). Dornier Thulio p-Tm:YAG may represent an attractive new laser platform, with comparable properties to TFL including decreased retropulsion, (Petzold et al., 2021b) smaller dust, (Petzold et al., 2021a) and improved ablation efficiency relative to Ho:YAG. (Petzold et al., 2021a; Kraft et al., 2022a; Solano et al., 2023) Moreover, the p-Tm:YAG laser has been shown to be effective in treating a wide range of human stone types. (Kwok et al., 2023). The Dornier Thulio p-Tm:YAG laser has been tested clinically in a limited fashion via pilot studies in URS (Panthier et al., 2023) and the RevoLix Hybrid Thulium Laset (HTL) was studied in mini-PCNL (Bergmann et al., 2023). However, limited research has directly compared its efficacy and safety and no prospective comparative trials have been published. This study aims to investigate whether Dornier Thulio p-Tm:YAG laser is non-inferior to TFL in terms of dusting ablation efficiency (J/mm³) and dusting ablation speed (mm³/s) for ureteroscopic stone treatment.

6. RESEARCH DESIGN AND METHODS

Patients will be identified based on operating room schedule, clinic visits or hospital admission. All patients will be counseled on standard treatment options – extracorporeal shock wave lithotripsy (ESWL), percutaneous nephrolithotomy (PCNL) and ureteroscopy (URS). The discussion regarding treatment options and subsequent care will not deviate from routine care. Those selecting URS will be enrolled to have data collected prospectively. Patients will be consented prior to surgery for collection of demographics, disease, perioperative, and postoperative data. Abdominopelvic computed tomography (CT) will be used to delineate pre-operative stone size, with measurements

captured in greatest axial and coronal dimensions. A preoperative abdominopelvic CT will be obtained if one is not available as suggested by American Urological Association guidelines. Urinalysis or urine culture will be obtained preoperatively as required in the guidelines. (Assimos et al., 2016) Preoperative alpha blocker will be used at surgeon discretion.

Patients will have flexible URS performed in standard fashion, without deviation from the standard of care. The patient will be brought to the operating room and given general or regional anesthesia per anesthesia and patient preference. The patient will be placed in lithotomy position and prepared and draped in standard fashion. Rigid cystoscopy will be performed and a flexible guidewire will be placed through the ipsilateral ureter to the kidney under fluoroscopic guidance. Any existing ureteral stent will be removed (if present). A second wire will be placed at the discretion of the surgeon. Ureteral dilation will be performed at the discretion of the surgeon. An access sheath will be placed (size and length per surgeon discretion). If sheath cannot be placed patient will be excluded from the study and remainder of the case completed at physician discretion. Flexible URS and laser lithotripsy will be performed using a dusting technique until the surgeon feels it is necessary to switch to fragmentation mode. The surgeon will report the estimated % of the case that was completed by dusting at the conclusion of the case. A 270 micron Thulium laser fiber will be utilized for patients in the TFL group and also a 272 micron p-Tm:YAG laser fiber will be utilized for patients in the p-Tm:YAG group.

Laser settings will be adjusted at the surgeons' discretion but begin at 0.3 J and 10 Hz (long pulse mode for Thulio and short pulse for TFL). (Petzold et al., 2021a) At the surgeon discretion the joules and/or frequencies can be increased by smallest increments available. If possible, a stone fragment will be removed and sent for stone analysis. An additional fragment may be sent for culture at the discretion of the surgeon. Adequacy of dusting will be defined as stone fragments smaller than the laser fiber diameter. A ureteral stent will be placed at the conclusion of the surgery. A string will be left on the stent at the discretion of the surgeon. Post-operative medical therapy will be an alpha receptor blocker to induce ureteral relaxation if not contraindicated for allergy, cataracts, or history of adverse reaction. Additionally, standard postoperative pain medications will be prescribed at the discretion of the treating surgeon.

The stent will be maintained for 2 to 21 days after surgery. Low-dose CT abdomen/pelvis will be performed at 6 weeks postoperatively to assess for stone-free rate, development or persistence of hydronephrosis/obstruction, and need for ancillary procedures. Telephone calls at 2, 4, and 6 weeks will be placed by the CRC to determine any unreported AEs. First clinic follow-up after stent removal will be performed at 8 weeks after stent removal. Telephone call at 2, 4 and 6 weeks will be made by CRC to determine any unreported AE's.

Lasing time (s), laser energy expended (J), and estimated % of the case completed with dusting will be recorded at the conclusion of the case from the laser data log.

All study procedures are standard of care except for the randomization aspect, which will randomly assign a patient to one of two laser groups, and data collection.

Demographic fields that will be obtained preoperatively include age, gender, ASA (American Society of Anesthesiologists) score (for comorbidity assessment), height, weight, body mass index (BMI), and primary or recurrent stone, prior stone composition(s). Disease fields that will be obtained include stone volume (calculated with maximal axial and coronal dimensions), average stone Hounsfield units, degree of hydronephrosis (mild/moderate/severe), and prior ureteral stenting or nephrostomy tube placement.

Perioperative fields will include total operative time, presence of preoperative alpha blockers, procedure time, laser time, setting of lithotripsy that was used most frequently during the case, total laser energy used, use of active fragment extraction (# of fragments beyond that for analysis/culture), 1st assist skill level (PGY level), use and size of ureteral access sheath, intra-operative complications, and treatment on any anticoagulation.

Postoperative fields will include length of hospitalization, postoperative complications, stone composition, need for ancillary procedures, stent duration, and stone-free status on postoperative low-dose CT imaging (axial slices 2.5mm and sagittal/coronal 3mm) using residual stone ABC grading (0 fragments, <2mm fragments, 2-4mm fragments) as recently recommended by Journal of Endourology. (Stern et al., 2023).

The trial will be a prospective, study of patients with renal stones 7-20 mm in size located at or above the level of the ureteropelvic junction. Total enrollment will be limited to 100 patients (50 ureteral and 50 renal) for the study with goal of 50 patients (25 ureteral and 25 renal) in each arm. This goal recruitment number is based on a power analysis for a noninferiority study utilizing a pre-determined non-inferiority margin of 20%, and was calculated to provide 90% power with a one-sided significance level of 0.025.

Table 1, adapted from (Solano et al., 2023), was constructed using results from recently published studies reporting ablation efficiency (J/mm³). The median ablation efficiency for TFL in the table was of 5.6 J/mm³ (Enikeev et al., 2021) with IQR 3-9.9. Assuming a normal distribution, the median and IQR values were used to estimate mean of 6.2 J/mm³ and standard deviation of 5.2 J/mm³. (Wan et al., 2014; Luo et al., 2018) Non-inferiority margin was set at 20% (6.2-1.2=5.0 J/mm³). Estimated mean difference between TFL and Tm:YAG ablation efficiencies was 0 based on a recent systematic review by an international expert in the field (Solano et al., 2023). Data was input into a validated sample size calculator <https://app.sampsize.org.uk/> as previously described. (Flight and Julious, 2016; Negida, 2020) A sample size of 24 participants per group (n=48 total) was found to provide 90% power to detect a non-inferiority margin of 20% with a one-sided significance level of 0.025.

In a separate power calculation using data from the only published in-vitro direct comparison of TFL to Tm:YAG revealed an average ablated weights across all laser configurations to be 0.61g (SD= 0.44 g) for p-Tm:YAG and 0.76g (SD= 0.51 g) for TFL. (Kraft et al., 2022b) Using a mean difference of 0.16g and a non-inferiority margin of 20% (0.76g-0.15g=0.61g) with a population SD of 0.47g, data was input into a validated sample size calculator <https://app.sampsize.org.uk/> as previously described. (Flight and Julious, 2016; Negida, 2020) A sample size of 24 participants per group (n=48 total) was found to provide 90% power to detect a non-inferiority margin of 20% with a one-sided significance level of 0.025.

| Laser | Reference | N | Stone size (mm ³) | Stone density (HU) | Laser on time (min) | Ablation speed (mm ³ /s) | Ablation efficacy (J/mm ³) |
|------------|----------------------------|--------------------|-------------------------------|-------------------------|---------------------|-------------------------------------|--|
| TFL | (Enikeev et al., 2021) | 14 9 | 179 (94-357) | 985 ± 60 | 1.2 (0.5-2.7) | 2.33 (1.33-4.65) | 5.6 (3-9.9) |
| | (Haas et al., 2023) | 56 | 288 (77-371) | 990 (726-1203) | 5.1 (1.7-7.3) | 8.05 (4.55-11.53) | 2.4 (1.1-3.2) |
| | (Korolev et al., 2021) | 2386 (1083 - 4202) | | | | | |
| | | | 900 (625-1275) | 5.31 (3.3-9.6) | 6.8 (4.6-12.5) | 3.38 (1.68; 5.36) | |
| | | 1186 (905-2317) | 1100 (750-1350) | 5.2 (1.95-8.8) | 5.1 (3-8.7) | 4.89 (2.77-7.44) | |
| | | | 1337 (878-3665) | 1170 (636-1300) | 5.9 (3.55-10.53) | 4.4 (3.4-7.6) | 4.21 (3.3-6.12) |
| | (Sierra et al., 2022) | 346 (147-1800) | 900 (400-1500) | 17.4 (13.2-24.4) | 0.3 (0.2-1.3) | 8.7 (4.8-65.2) | |
| | | | 1125 (294-4000) | 950 (725-1125) | 26.38 (17-57.1) | 0.7 (0.4-1.2) | 14.3 (7.8-24.7) |
| | (Taratkin et al., 2022) | 15 3 | 279.6 (139.4-615.8) | 1,020 ± 382 (250-1,900) | 2.7 (1.6-6.6) | 1.7 (1.0-2.8) | 13.3 (7.3-20.9) |
| | (Vaddi et al., 2022) | 12 6 | 1061.85 ± 806.81 | 985.82 ± 302.57 | 19.78 ± 12.32 | 0.86 ± 0.31 | 14.35 ± 5.70 |
| Ho: YAG | (Haas et al., 2023) | 52 | 319 (59-521) | 1028 (808-1286) | 4.8 (1.2-6.7) | 10.46 (3.41-14.46) | 1.6 (0.7-2.2) |
| | (Ventimiglia et al., 2021) | 30 | 1599 (630-3502) | 1040 (753-1275) | - | 0.7 (0.4-0.9) | 19 (14-24) |
| | (Patil et al., 2022) | 51 | 2770.54 ± 1977.06 | 1211.68 ± 259.81 | 11.30 ± 8.23 | 4.64 ± 2.07 | 9 ± 5 |
| | (Azilgareeva et al., 2022) | 25 | 508.9 (293.2-628.3) | 1124.0 ± 329.0 | 15.0 (11.2-18.3) | 0.6 (0.5-0.9) | 30.8 (22.8-41.2) |

The electronic data will be stored in the REDCap (Research Electronic Data Capture) application (16,17). REDCap is a stand-alone system with no interaction or connectivity to other systems, and the database is located behind the UCSD firewall. Users must have a UCSD provided ID/password to connect to REDCap and their ID must be specifically

authorized in order to access an individual study's data. All changes to the data, and each "record viewed" is logged back to the individual ID with a timestamp. When the case report forms are configured, each field has an attribute that can be set to flag it as an "identifier". This "identifier" is used by REDCap to control certain actions related to the field. REDCap also has several built-in functions to control the exporting of identifying information. Individual users are each granted specific export rights, including – None, De-Identified, and Full. Additional export de-identification options include removing identifiers and dates, hashing IDs and date shifting.

Demographic data, pre-operative, and post-operative data will be summarized using mean, median and quartiles (continuous variables) and frequency and percent (categorical variable).

Intention-to-treat analysis will be performed. Non-inferiority analysis will be conducted for the primary endpoints, with a pre-specified non-inferiority margin of 20%.

Secondary endpoints will be compared using appropriate statistical tests (e.g., t-test, chi-square test). All analyses will be performed using a statistical software package (e.g., SPSS).

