4. SPECIFIC AIMS/HYPOTHESES

Our primary objective is to assess stone dusting ablation efficiency (Joules/stone volume ablated) between both laser systems *in vivo* for ureteroscopic stone treatment (Ventimiglia et al., 2021, 2023; Corrales and Traxer, 2022). Secondary objectives include assessing stone dusting ablation speed (stone volume ablated/lasing time), stone-related clinical outcomes, effect of hard stones (>1000HU) on ablation efficiency, and safety/complication profile of both laser systems.

We hypothesize that dusting ablation efficiency and speed of the p-Tm:YAG laser will be non-inferior to TFL for the treatment of renal stones totaling 7-20 mm in diameter with similar clinical and safety/complication outcomes.

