7. RESEARCH PARTICIPANTS

We plan to enroll 100 participants in this study at the University of California, San Diego.

Inclusion criteria:

- Solitary renal stone 7 to 20 mm in size or in the case of multiple stones the conglomerate diameter (additive maximal diameter of all stones on axial imaging of computed tomography) of 7-20 mm is required
- Must be a suitable operative candidate for flexible ureteroscopy per American Urological Association guidelines
- Must be 18 years or older
- Must be able to give consent
- Bilateral ureteroscopy will be permitted but only the first side (per surgeon discretion) will be included in the study
- Surgeons participating in the study must be urological attending surgeons or fellows with subspecialty training in Endourology

Exclusion criteria:

- Concomitant stones in the ureter
- Prior ipsilateral upper urinary tract reconstructive procedures or history of ipsilateral ureteral stricture
- Prior radiotherapy to the abdomen or pelvis
- Neurogenic bladder or spinal cord injury
- Pregnancy
- Untreated UTI

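### The protocol computes stone volume, the denominator of the primary endpoint, from two maximal CT diameters that can lie on the same axis and so do not determine a volume

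*Protocol*

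**What the plan says.** Protocol section 4 sets the primary endpoint: "Our primary objective is to assess stone dusting ablation efficiency (Joules/stone volume ablated) between both laser systems". The same volume is the numerator of a second outcome, "stone dusting ablation speed (stone volume ablated/lasing time", which section 4 also includes in the non-inferiority hypothesis.

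Section 6 describes how stone size is read from the pre-operative CT, with measurements "captured in greatest axial and coronal dimensions". Its list of disease fields then gives "stone volume (calculated with maximal axial and coronal dimensions". No other stone volume is collected. The section names no third diameter, volume formula or segmentation method, and does not require the two dimensions to be perpendicular. Sagittal images are mentioned only for the post-operative low-dose CT.

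The energy side of the ratio comes from the laser log: "Lasing time (s), laser energy expended (J), and estimated % of the case completed with dusting will be recorded". It does not depend on how the stone is measured.

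For multiple stones, the inclusion criteria in section 7 use the "additive maximal diameter of all stones on axial imaging of computed tomography". That rule decides eligibility. The protocol does not say how volume is obtained when there is more than one stone.

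**The concern.** An ellipsoid's volume needs three orthogonal diameters. The axial plane holds the left-right and front-back axes; the coronal plane holds the left-right and head-foot axes. When a stone is longest from left to right, the greatest axial and greatest coronal dimensions are the same line, and neither of its other two axes is recorded. When it is longest in another direction, two axes are captured and the third is not. The computed volume then depends on how the stone happens to lie, which has nothing to do with the laser.

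At stake is the precision of the two outcomes named in the hypothesis and, under conditions set out below, the meaning of the margin. A formula written later cannot recover a diameter that was never recorded; the CT would have to be read again.

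**Working it through.** **The plan's own figures.** The protocol gives no worked stone volume to reproduce. The figures that bear on the point are in section 6: "estimate mean of 6.2 J/mm³ and standard deviation of 5.2 J/mm³", from a median of 5.6 with IQR 3-9.9, and "Non-inferiority margin was set at 20% (6.2-1.2=5.0 J/mm³". The margin reproduces: 0.20 x 6.2 = 1.24, rounded to 1.2.

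**Assumptions not in the documents.** Stones are ellipsoids of the shapes shown. The unmeasured diameter is filled in as the smaller, the geometric mean or the larger of the two measured maxima, d1 and d2.

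**Step 1: one stone, aligned with the body axes.** A 12 x 8 x 6 mm stone has true volume pi/6 x 12 x 8 x 6 = 301.6 mm³.
- Long axis left-right: d1 = 12 and d2 = 12, so any filling rule gives pi/6 x 12³ = 904.8 mm³. Ratio 1728/576 = 3.00; J/mm³ reads at 0.33 of its true value.
- Long axis front-back or head-foot: the maxima are 12 and 8. Filling with 8 gives 768/576 = 1.33, the geometric mean gives 1.63, and filling with 12 gives 1152/576 = 2.00. J/mm³ reads at 0.75 to 0.50 of its true value.

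**Step 2: random orientation.** For 20,000 orientations per shape, each maximum was taken on the central section of its plane. The ratio is (d1 x d2 x third)/(a x b x c), where a, b and c are the true diameters. Entries are the median (5th-95th percentile).

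| Shape (mm) | Third = smaller | Third = larger |
|---|---|---|
| 12 x 8 x 6 | 1.41 (1.12-2.57) | 1.92 (1.27-2.72) |
| 12 x 10 x 9 | 1.17 (1.07-1.52) | 1.33 (1.15-1.55) |
| 14 x 7 x 7 | 1.22 (0.95-3.15) | 1.94 (1.15-3.42) |

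The medians run from about 1.2 to 1.9. Volume is understated in 0-2% of cases for most combinations, but in 19% for the 14 x 7 x 7 mm stone when the smaller maximum is reused. The SD of the log ratio runs from 0.09 to 0.38 across the shapes, and is 0.22-0.23 when shapes are mixed at random. A separate calculation with axis-aligned stones, shorter axes 50-100% of the longest, gave 0.24-0.28.

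**Step 3: cost in precision.** On the log scale the quoted IQR implies an SD of (ln 9.9 - ln 3)/1.349 = 0.885. If an independent error with SD e is added, the required n is multiplied by (0.885² + e²)/0.885².
- e = 0.24: 1 + 0.0576/0.7832 = 1.07.
- e = 0.28: 1 + 0.0784/0.7832 = 1.10.
- Extremes from step 2: e = 0.09 gives 1.01 and e = 0.38 gives 1.18.

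This treats 0.885 as free of this error. If the source study measured volume in the same way, its spread already contains part of it.

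**Step 4: the margin, if absolute.** A common overstatement f divides the mean by f, so a fixed 1.2 J/mm³ becomes 1.2 x f/6.2 of the observed mean: 19% at f = 1, 23% at 1.2, 29% at 1.48 and 37% at 1.9. If the margin is applied as a ratio, f cancels.

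**The case against.** **The wording may be shorthand.** Maximal axial and coronal dimensions could mean axial length and width plus coronal height, which are three orthogonal diameters. If so, the problem disappears apart from the unstated formula. The text does not settle this. Taking the greatest dimension in each plane reads more naturally as one number per plane, but the benign reading cannot be excluded.

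**No formula is given.** A reader might conclude that volume is always overstated. The documents do not support that: the direction depends on how the third diameter is filled in and on the coefficient used, and step 2 shows some understatement. This part of the objection stands. The formula itself could be left to a later plan; the choice of what is measured could not, because the protocol already fixes it.

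**Multiple stones.** A reader might infer that volume is built on the summed diameter, which would overstate it 4-fold for two equal stones (two of 10 mm: 2 x 523.6 = 1047 mm³ against pi/6 x 20³ = 4189 mm³) and 9-fold for three. The protocol uses that sum only for eligibility, so these figures describe a rule it does not contain. What remains is that summing volumes stone by stone is not stated.

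**Bias between arms.** A reader might expect a false difference between lasers. Size is read pre-operatively, allocation is randomised, and section 8 keeps surgeons blind to the laser until the operating room, so the error should be alike in both arms. Chance imbalance in stone shape is ordinary sampling variation, which the test already allows for.

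**Margin.** The analysis text in section 6 states the margin only as 20%; 1.2 J/mm³ appears in the sample-size reasoning. The documents do not say how the baseline study measured volume. Table 1 also shows TFL values from 2.4 to 14.35 J/mm³, so the 6.2 is uncertain for larger reasons. Step 4 is therefore a conditional possibility.

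**Conclusion.** The point holds as a weakness in a stated measurement rule. Read as written, two in-plane maxima do not determine the volume on which J/mm³ and ablation speed both depend. With the third diameter filled in from the two, volume is usually overstated, by a median of about 1.2 to 1.9-fold and about 3-fold for an elongated transverse stone. These sizes rest on assumed ellipsoid shapes and on the filling rule; that both planes share the left-right axis does not.

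The consequence is limited. It is added noise, about 7-10% more required n at an error log-SD of 0.24-0.28, with no systematic advantage to either laser. A shift of scale against the margin arises only if 1.2 J/mm³ is applied as an absolute margin and the baseline study measured volume differently; the documents establish neither. This is a cheap improvement and does not undermine the comparison.

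**What to change.** In both places in section 6 (the CT measurement and the disease fields), state that each stone is measured in three orthogonal diameters on the pre-operative CT, or by CT segmentation. Give the formula pi/6 x length x width x height, and say that volumes are summed over stones when there are several. Require the measurement to be complete before the allocation is opened. Leave the summed diameter in section 7 as an eligibility rule. If axial length and width plus coronal height were meant all along, say so and add the formula.

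The cost is a change of wording and one more caliper reading per stone on a CT that is already available. Where a patient has been measured by the two-diameter rule, the stored pre-operative CT can be read again.

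### Half of the planned enrolment is ureteral, but the protocol admits only renal stones, so no eligible patient can fill those 50 places

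*Protocol*

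**What the plan says.** Section 6 (Research Design and Methods) describes the trial as one of "patients with renal stones 7-20 mm in size located at or above the level of the ureteropelvic junction". The next sentence sets the numbers: "Total enrollment will be limited to 100 patients (50 ureteral and 50 renal) for the study". The same division is then carried down to the treatment groups, "with goal of 50 patients (25 ureteral and 25 renal) in each arm". It then gives their source: "This goal recruitment number is based on a power analysis for a noninferiority study". The analysis reported in the following paragraph concludes: "A sample size of 24 participants per group (n=48 total) was found to provide 90% power". A second calculation in the same section, from in-vitro data, reports the same 24 per group.

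Section 4 (Specific Aims/Hypotheses) expects the pulsed Tm:YAG laser to be "non-inferior to TFL for the treatment of renal stones totaling 7-20 mm in diameter". Section 7 (Research Participants) gives the total without a split: "We plan to enroll 100 participants in this study". Its first inclusion criterion is "Solitary renal stone 7 to 20 mm in size", or several stones whose summed diameter falls in the same range. Its first exclusion criterion removes patients who also have a stone in the ureter. The protocol contains no eligibility criteria for a ureteral cohort.

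**The concern.** The enrolment target and the eligibility criteria describe different trials. Site staff cannot satisfy both, and each way out gives a different study:

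- Fill the split: up to 50 patients who fail eligibility are enrolled, and two stone locations are pooled in the primary J/mm³ comparison.
- Apply eligibility and keep the renal limit of 50: recruitment ends at 25 per arm.
- Apply eligibility and the unsplit total in Section 7: recruitment ends at 50 renal patients per arm.

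The analysed population and the precision of the primary comparison depend on which reading is used. Patients enrolled outside eligibility cannot be undone later, so the question should be settled before further enrolment.

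**Working it through.** **1. Does the split add up?** Yes: 50 + 50 = 100 in total and 25 + 25 = 50 per arm, with 2 × 50 = 100. The total and per-arm figures agree, so this is not a slip in a single number.

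**2. Who can fill the ureteral places?** Set the split against Section 7:

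| Patient | Renal-stone inclusion | Ureteral-stone exclusion | Eligible |
|---|---|---|---|
| Renal stone only | met | not triggered | yes |
| Ureteral stone only | not met | – | no |
| Renal and ureteral stones | can be met | triggered | no |

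Eligible patients for the ureteral places: 0 of 50. Stones at the ureteropelvic junction cannot be the ureteral group, because Section 6 itself calls stones at or above that level renal.

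**3. Does the power analysis produce 100?** The protocol's own result is 24 per group, 2 × 24 = 48. The stated enrolment exceeds this by 100 − 48 = 52 patients, with no reason given. One calculation per stone location would give 2 × 48 = 96, close to 100, but the protocol does not say this was done.

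**4. What hangs on 25 or 50 per arm?** Inputs from Section 6: SD 5.2 J/mm³, margin 1.2 J/mm³, true difference 0, one-sided significance level 0.025. Allocation is 1:1 (Section 8).

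The 95% confidence interval half-width for a difference in means is t(0.975, 2n − 2) × 5.2 × √(2/n):

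- n = 25: 2.011 × 5.2 × √(2/25) = 2.96 J/mm³
- n = 50: 1.984 × 5.2 × √(2/50) = 2.06 J/mm³

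Power for non-inferiority (noncentral t) is 12.3% at 25 per arm and 20.7% at 50. The normal approximation gives 12.6% and 21.0%.

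**5. Is the low power due to the split?** Not mainly. With these inputs, 90% power needs 2 × (1.960 + 1.282)² × (5.2/1.2)² ≈ 395 per group, not 24. That is a separate sample-size error. Judged by the protocol's own 24 per group, 25 per arm would be enough.

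**6. Source of the planning values.** The mean of 6.2 and SD of 5.2 J/mm³ derive from a TFL series whose title in the reference list (Section 13) says it treated ureteral stones, a population that Section 7 does not admit.

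**The case against.** The contradiction itself is hard to dispute, and nothing else in the protocol resolves it. The objections concern what follows from it.

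**The split may be deliberate.** It gives 25 per arm at each location, just above the calculated 24, so the sponsor may have planned two cohorts and left the eligibility text unrevised. Deleting the split would then remove the only visible source of the 100. This is a fair inference and a reason for the sponsor to confirm the intent. However, no eligibility criteria, hypothesis or analysis for a ureteral cohort appears anywhere, so the text supports a renal trial far better.

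**Section 7 is only silent on a split, and silence is not conflict.** This is true of the sentence giving the total. But under Section 7's own criteria all 100 would be renal, while Section 6 limits renal patients to 50. Read with its criteria, Section 7 does conflict with Section 6.

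**Screening would in practice admit only renal patients.** Probably so, which makes enrolment of ineligible patients the less likely outcome. It still leaves open whether recruitment stops at 50 or 100.

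**The power figures belong to another error, and enrolling more than a calculated minimum is allowed.** Both points stand. Low power is not offered here as a consequence of the split, and what is wrong about the 100 is that it is attributed to an analysis that gives 48. The half-widths use an SD from a ureteral series, so they show the relative loss of precision and are not a forecast.

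**Conclusion.** The point holds and should be corrected. As written, 50 of the 100 places, 25 of 50 in each arm, have no eligible patient. This rests on the text alone and needs no statistical assumption.

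The consequence for the primary comparison is a choice between 25 and 50 renal patients per arm, with interval half-widths of about 2.96 and 2.06 J/mm³. Those figures assume the protocol's SD of 5.2 J/mm³ in both arms and an unadjusted difference in means. The protocol does not settle which number was intended. The shortfall from 90% power is a separate matter, and this finding would stand if the sample-size calculation were sound.

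**What to change.** Reconcile the enrolment sentence in Section 6 with the eligibility criteria in Section 7, after the sponsor confirms which population is intended.

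The title, the hypothesis, the inclusion and exclusion criteria and the unsplit total in Section 7 all fit a renal-stone trial. The simplest amendment is therefore to delete both ureteral/renal splits from Section 6 and state 100 renal-stone patients, 50 per arm. In the next sentence, say that the reported analysis gives 24 per group (48 in total) and give the actual reason for enrolling 100. Add that the planning mean and SD come from a ureteral-stone series, and restate power for the per-arm number kept.

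The cost is a wording amendment to two sentences and a short note on the planning values. Total enrolment stays at 100 and eligibility is unchanged. The restated power will fall well below 90%, because of the separate sample-size error.

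If a ureteral cohort was in fact intended, the cost is larger: eligibility, hypothesis and analysis would all have to be rewritten to admit it.

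### The 20% non-inferiority margin for J/mm³ is converted to an absolute 1.2 on the favourable side of the reference, and the analysis text never fixes its scale or direction

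*Protocol*

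**What the plan says.** All of this is in Protocol section 6 (Research Design and Methods).

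- **Planning distribution.** The TFL reference is one row of Table 1, with median 5.6 and IQR 3 to 9.9 J/mm³. "Assuming a normal distribution, the median and IQR values were used to estimate mean of 6.2" J/mm³, with "standard deviation of 5.2 J/mm³". The assumed true difference between lasers is 0.
- **Margin in the sample-size text.** "Non-inferiority margin was set at 20% (6.2-1.2=5.0 J/mm³". This is the only place where the percentage for J/mm³ becomes a number.
- **Claimed size.** "A sample size of 24 participants per group (n=48 total) was found to provide 90% power", at one-sided 0.025. Planned enrolment is 100, or 50 per arm.
- **Margin in the analysis text.** The primary endpoints get a non-inferiority analysis "with a pre-specified non-inferiority margin of 20" percent. No scale, reference value, direction or test is given.

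Section 4 defines the primary measure as joules per volume of stone ablated, so a lower value means a more efficient laser. It also hypothesises non-inferiority on ablation speed, where a higher value is better.

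**The concern.** A percentage margin and an absolute margin agree only at the reference value used for the conversion. Here that value is an assumed TFL mean of 6.2. Table 1 gives little reason to expect the TFL arm to land there. The row behind 6.2 comes from a series whose title concerns ureteral stones, while section 7 requires renal stones and excludes concomitant ureteral ones. The rows at 13.3 and 14.35 come from series of retrograde intrarenal surgery. If the absolute figure is used, the strictness of the trial depends on where TFL happens to fall.

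The written limit also points the wrong way. For J/mm³ a worse laser has a higher value, so a 20% allowance for inferiority should lie above 6.2. Subtracting suits the protocol's second calculation, on ablated weight, where more is better. It does not suit J/mm³. Taken literally, a limit of 5.0 asks the new laser to beat TFL by 1.2. Tested on that side the other way round, as if higher were better, the rule would pass more easily the more energy the new laser needed.

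**Working it through.** **1. The planning mean and SD reproduce.** From quartiles 3, 5.6, 9.9 and n = 149 (Table 1), the sample-size-weighted mean is 6.20 (the simple average of the three is 6.17). The SD is (9.9 − 3)/1.349 = 5.11, or 5.17 with the small-sample correction. The protocol's 6.2 and 5.2 agree.

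**2. The stated size does not follow from a margin of 1.2.** Per arm, n = 2 × SD² × (1.96 + 1.2816)² / margin².

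- Margin 1.2: 2 × 5.2² × 10.507 / 1.44 = 395 (396 by noncentral t), not 24.
- Of the margins tried (1.2, 1.24 and 5.0), only 5.0 gives 24: 2 × 27.04 × 10.507 / 25 = 23, or 24 by t.
- Power at margin 1.2 with 50 per arm: SE = 5.2 × √(2/50) = 1.04; Φ(1.2/1.04 − 1.96) = Φ(−0.81) = 21%. With 24 per arm it is 12%.

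**3. How well the normal shape fits.** Φ(−6.2/5.2) = 11.7% of patients would have a negative J/mm³. In the 5.6 row the quartiles lie 2.6 below and 4.3 above the median; in logs the distances are 0.62 and 0.57.

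**4. What 1.2 means across the TFL rows of Table 1.** 1.2 divided by the reported TFL value:

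| TFL value (J/mm³) | 1.2 as a percentage |
|---|---|
| 2.4 | 50% |
| 3.38 | 36% |
| 5.6 | 21% |
| 8.7 | 14% |
| 13.3 | 9.0% |
| 14.35 | 8.4% |

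At the assumed mean of 6.2 it is 19.4%.

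**5. Simulated consequences, if 1.2 is used on raw means.** Lognormal data with each row's median and log SD = ln(Q3/Q1)/1.349; 50 per arm; one-sided 0.025; non-inferior if the upper confidence limit lies below the margin. Entries are the proportion of trials declaring non-inferiority.

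| Row | Truth | Fixed 1.2, raw means | 20% of the true mean, raw means | Ratio 1.20, log scale |
|---|---|---|---|---|
| 5.6 (3–9.9) | equal | 11% | 17–18% | 17% |
| 13.3 (7.3–20.9) | equal | 6% | 22% | 21% |
| 2.4 (1.1–3.2) | new laser 20% worse | 16% | 3% | 2.5% |

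The last two columns nearly coincide, so the gap comes from the size of the margin and not from the shape of the data.

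**6. Error rate against its own margin.** With a true difference of exactly 1.2, TFL means from 2.4 to 14.35 and log SD 0.885, the raw-scale test passes in 2.6% to 4.2% of trials at 50 per arm.

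**7. Power on a ratio scale.** Log SD = ln(9.9/3)/1.349 = 0.885. With 50 per arm, SE = 0.885 × √(2/50) = 0.177.

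- Limit 1.20: Φ(0.182/0.177 − 1.96) = 18%; 90% power needs 2 × 0.885² × 10.507 / 0.182² ≈ 496 per arm.
- Limit 1.25: Φ(0.223/0.177 − 1.96) = 24%; 90% power needs about 331 per arm.

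**The case against.** **The analysis text does not say 1.2.** It fixes only 20%. The normal assumption and the subtraction serve the sample-size calculation, and the test and its scale may be set in a statistical analysis plan that is not shown. This stands: a reader might infer that raw means will be tested against a fixed 1.2, but the protocol does not say so. What remains is that the only conversion it gives is absolute and on the wrong side, and that the margin itself is a design choice the protocol has undertaken to pre-specify.

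**Non-normality is not the problem.** A reader might conclude from the 11.7% below zero that a test on means would fail. The simulation does not support that: with a raw margin set at 20% of the true mean, raw and log analyses have almost the same power. This stands.

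**The test does not lose its error rate.** Against a true difference of 1.2 it stays between 2.6% and 4.2%. The 16% arises only when the yardstick is a true 20% deficit. This stands too, although a 20% deficit is what the protocol says it wants to rule out.

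**The lognormal shape is selective.** The 2.4 row is skewed the other way (1.3 below the median, 0.8 above), and the 13.3, 3.38 and 4.89 rows are no more symmetric in logs than on the raw scale. Modelled as lognormal, the 2.4 row has mean 3.28, above its own upper quartile. With a TFL mean of 2.4 and log SD 0.885 the 16% becomes 31%. The direction holds; the exact figures do not. The 50%-to-8% range needs no shape assumption.

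**The sample-size discrepancy is larger.** True, and it is a separate defect. Correcting n would not make 1.2 equal 20% at other TFL values. Only a margin of 5.0 was found to give 24, but the protocol does not say what was entered, so that explanation remains a conjecture.

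**Conclusion.** The point holds in a limited form. The protocol gives the 20% margin a numerical meaning for J/mm³ in one place only, as an absolute 1.2 around an assumed mean of 6.2, with the limit on the favourable side. It then leaves scale and direction open where the analysis is described. On the protocol's own table, 1.2 is 50% down to 8% of the TFL value. If it is carried into the analysis, a 20% worse laser could pass too often where TFL values are low (about 16% for the 2.4 row), and equal lasers would rarely pass where they are high (about 6% for the 13.3 row). Those two figures assume lognormal data and 50 per arm.

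The documents do not show that the final test will use 1.2, that skewness alone harms the test, or that the test fails against its own margin. The claim of "90% power to detect a non-inferiority margin of 20% with a one-sided significance level of 0.025" is not met on either scale: at 50 per arm, power is about 21% on the protocol's raw inputs and about 18% for a ratio of 1.20. At 24 per arm the figures are about 12% and 11%.

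**What to change.** State the margin as a ratio, with its direction, in both the sample-size and analysis paragraphs of section 6. For example: analyse log(J/mm³), and declare p-Tm:YAG non-inferior if the upper 97.5% confidence limit of the p-Tm:YAG/TFL geometric mean ratio is below 1.20, lower values being better. For ablation speed, require the lower 97.5% confidence limit of the same ratio to be above 0.80. If the two limits should be symmetric on the log scale, use 1.25 (1/0.80) for J/mm³ instead of 1.20. Choose one and give the reason before data are seen. Remove the 5.0 limit.

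Replace the 90% power statement with the value for the planned 50 per arm: about 18% for a limit of 1.20, or 24% for 1.25, stating that the log SD of 0.885 is assumed from the IQR 3 to 9.9. If the raw scale is kept, the figure is about 21% and the margin's meaning still has to be settled.

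The change itself is wording. The cost is that results are reported as a ratio of geometric means rather than a difference in means, and that the stated power becomes much less favourable. The sponsor would then have to decide whether a trial of this size can support a non-inferiority claim.
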